7. RETENTION OF SPECIMENS FOR FUTURE USE

All specimens collected as part of this trial may be stored indefinitely for future research. These samples may be used to learn more about influenza infection and other diseases but will not be used for genetic testing. These samples will not be sold or used to make commercial products. Samples will be stored only with the subject's permission, which is

a requirement for participation in the study. The subject may withdraw permission for future use of specimens at any time. If a subject withdraws his or her permission for future use of specimens, those specimens will be destroyed. All samples stored will be labeled with the subject's study identification (ID) number, which cannot identify the study subject but is linkable to other research databases (e.g., from questionnaires, clinical assessments, logbooks, etc.) generated by the main study. The database will contain only the study subject's ID number. A master log linking the study subject ID number to the name of the subject will be maintained in a password protected database system with access limited to authorized research team members.

At the completion of the protocol (termination), samples and data will either be destroyed, or transferred to a repository (JHSPH IRB protocol R22.05.04.29.A2). In the future, other investigators (both at NIH and outside) may wish to study these samples and/or data. In that case, IRB approval must be sought prior to any sharing of samples. Any clinical information shared about the sample with or without patient identifiers would similarly require prior IRB approval. The research use of stored, unlinked, or unidentified samples (for example, as a standard for immunological analyses) may be exempt from the need for prospective IRB review and approval. Exemption requests will be submitted in writing to the NIH Office of Human Subjects Research, which is authorized to determine whether a research activity is exempt.

8. SAFETY AND ADVERSE EVENT REPORTING

8.1 Definitions

8.1.1 Adverse Events

An adverse event (AE) is any untoward medical occurrence in an investigational subject following receipt of an investigational drug, regardless of causality. Therefore, an AE can be any unfavorable and unintended sign (including an abnormal laboratory finding), physical exam, symptom, or disease temporally associated with the use of the investigational vaccine, whether or not related to it. Exacerbation of pre-existing conditions and intercurrent illnesses will be recorded as AEs. Stable chronic conditions that are present prior to enrollment and do not worsen are not considered AEs but will be accounted for in the subject's medical history. If a diagnosis is clinically evident or subsequently determined, the diagnosis rather than the individual signs and symptoms or lab abnormalities will be recorded as the AE.

A laboratory abnormality that is not included in the solicited AEs will be reported as an AE if it results in an intervention. Interventions include, but are not limited to, treatment discontinuation, dose reduction/delay, additional assessments (including repeat testing at a later time point if not specified in this protocol), or concomitant treatment. In addition, any medically important laboratory abnormality may be reported as an AE, at the discretion of the investigator. This could include a laboratory result for which there is not an intervention, but the abnormal value suggests a disease or organ toxicity. If the laboratory abnormality is the clinical sequela of a clinical condition, the diagnosis or

medical condition should be reported as the AE (e.g., renal failure, hematuria) rather than the laboratory abnormality (e.g., elevated creatinine, urine red blood cell increase).

8.1.2 Solicited Adverse Events (Protocol-Specified Adverse Events)

AEs will be categorized as Solicited AEs and Other AEs. Solicited AEs are predefined AEs that can potentially occur after vaccine administration. Reactogenicity events are solicited adverse events that occur in the first 7 days after vaccination. The following will be considered solicited AEs for subjects receiving the Monovalent Influenza Subvirion Vaccine (H5N1):

1. Fever $\geq 100.4^{\circ}\text{F}$ (38°C) oral
2. Headache
3. Malaise
4. Nausea
5. Myalgia
6. Injection pain
7. Injection site erythema
8. Injection site swelling
9. Injection site induration
10. Injection site pruritus

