8.1.3 Unsolicited Events

AEs that are not specifically listed in Section 8.1.2 and not documented in the screening medical history as pre-existing conditions will be categorized as “Other AE’s and identified by asking subjects about any new diagnoses, acute illnesses, worsening of a pre-existing condition, visits to the physician, ER, or hospital, medication use and indication.

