11.4.3 Immunization

Possible local vaccine reactions include pain, swelling, erythema, induration or pruritus at the injection site. Systemic reactions such as fever, chills, headache, fatigue, malaise, and myalgia may also possibly occur, with some reactions moderate or severe. A placebo-controlled trial of the H5N1 inactivated vaccine (12) showed that overall, the vaccine was generally well tolerated. The most common AE following immunization was mild pain at the injection site. Tenderness was also commonly reported. Less frequently, subjects reported malaise, myalgia or headache, although those symptoms were not statistically greater in the vaccinated group compared to the placebo group. Most reported AEs were mild (84%), some were moderate, and few were severe.

It is possible that a subject may experience a reaction that is severe or even life threatening, including, but not limited to an immune/allergy mediated response.

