Headache	No interference with activity	Repeated use of non-narcotic pain reliever > 24 hours or some interference with activity	Significant; any use of narcotic pain reliever or prevents daily activity	ER visit or hospitalization
Fatigue/Malaise	No interference with activity	Repeated use of non-narcotic pain reliever > 24 hours or some interference with activity	any use of narcotic pain reliever or prevents daily activity	ER visit or hospitalization
Myalgia	No interference with activity	Repeated use of non-narcotic pain reliever > 24 hours or some interference with activity	any use of narcotic pain reliever or prevents daily activity	ER visit or hospitalization

* Subject should be at rest for all vital sign measurements.

** When resting heart rate is between 60 – 100 beats per minute. Use clinical judgment when characterizing bradycardia among some healthy subject populations, for example, conditioned athletes.

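### Tenderness and chills, which Section 11.4.3 names for this vaccine, are neither solicited nor given an Appendix B row, so they fall outside any reactogenicity summary and may be less completely captured

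*Combined protocol and SAP*

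**What the plan says.** The secondary objective (Sections 2.2 and 10.5) is to compare the reactogenicity of the H5N1 vaccine between prior pLAIV recipients and naïve subjects. Section 8.1.2 defines the term: "Reactogenicity events are solicited adverse events that occur in the first 7 days after vaccination". Section 8.2 repeats the restriction. The list in Section 8.1.2 has ten entries: fever, headache, malaise, nausea, myalgia, and injection-site pain, erythema, swelling, induration and pruritus.

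Section 11.4.3 describes what may follow immunization. On local reactions: "Possible local vaccine reactions include pain, swelling, erythema, induration or pruritus at the injection site". On systemic reactions: "Systemic reactions such as fever, chills, headache, fatigue, malaise, and myalgia may also possibly occur, with some reactions moderate or severe". Of the earlier placebo-controlled trial it adds, after naming mild injection-site pain as the most common event: "Tenderness was also commonly reported".

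Under Section 8.1.3, events off the list are Other AEs, "identified by asking subjects about any new diagnoses, acute illnesses, worsening of a pre-existing condition", together with questions on health-care visits and medication use. Section 8.4 grades solicited AEs with Appendix B and all AEs with Table 2. Appendix B has a joint row labelled "Fatigue/Malaise" and no row for tenderness or chills. The secondary endpoint in Section 10.6 is the number of vaccine-related adverse events, compared between cohorts.

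**The concern.** The solicited list is the instrument for the secondary objective. A reaction missing from it is outside reactogenicity by definition, even when it occurs on Day 1 and is recorded. Tenderness is one that the protocol itself calls common with this vaccine, and chills is one that it warns of. The protocol therefore expects reactions that its own reactogenicity measure leaves out.

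Two things are at stake. A summary built on Section 8.1.2 would describe a narrower set of reactions than Section 11.4.3 does. And because tenderness and chills are sought only through general questions in an open-label study, their capture depends more on what subjects mention unprompted. That may differ between recalled trial participants and new recruits.

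**Working it through.** The plan states no figure on this point and none can be recomputed. The check is a comparison of terms across Sections 8.1.2, 8.1.3, 8.4, 10.6, 11.4.3 and Appendix B.

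**Step 1: match the terms.**

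| Source within 11.4.3 | Terms named | On the 8.1.2 list | Not on the list |
|---|---|---|---|
| Local reactions | 5 (pain, swelling, erythema, induration, pruritus) | 5 | 0 |
| Systemic reactions | 6 (fever, chills, headache, fatigue, malaise, myalgia) | 4 | 2 (chills, fatigue) |
| Reported from the earlier trial, not named above | 1 (tenderness) | 0 | 1 |
| Total | 12 | 9 | 3 |

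The nine matches leave one of the ten solicited terms, nausea, with no counterpart in Section 11.4.3 (10 − 9 = 1). The two lists differ in both directions.

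**Step 2: look up the three unmatched terms in Appendix B.**

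| Term | 8.1.2 | Appendix B | Nearest solicited item |
|---|---|---|---|
| Tenderness | absent | no row | injection pain |
| Chills | absent | no row | fever |
| Fatigue | absent | joint row with malaise | malaise |

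Tenderness and chills have no place in either. Fatigue has a grading row shared with a solicited term, so it is probably recorded under malaise. That is a wording mismatch.

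**Step 3: trace an unlisted event through the plan.** A subject has chills on Day 1. Under Section 8.1.3 this is an Other AE. It can be picked up in the first 30 minutes of observation, by a call to the study clinician, or at the Day 7 visit, where Section 6.8 requires an interim history directed at complaints and adverse events and an evaluation of the injection site. Section 6.8 and Appendix A describe no symptom diary, and the Section 8.1.3 questions name no symptom. If recorded within 28 days, the event is graded with Table 2 and, if judged related, counts in the Section 10.6 endpoint. It does not enter a reactogenicity summary as defined in Section 8.1.2.

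**Step 4: check what grading depends on the classification.** Table 2 sets Grade 3 at activities of daily living below 50% of baseline. For headache, fatigue/malaise and myalgia, Appendix B sets Grade 3 at use of a narcotic pain reliever or prevention of daily activity. The scales are not the same. Halting rule 4 in Section 8.7 counts related Grade 3 systemic AEs, so moving chills onto the solicited list without saying which scale applies would leave the input to that rule unclear.

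**The case against.** The strongest reply is that little is lost. The Section 10.6 endpoint is not limited to solicited or 7-day events, so a related chill or tenderness recorded as an Other AE is still compared between cohorts. All non-serious AEs are recorded for 28 days, Table 2 can grade any of them, and the 30-minute and Day 7 contacts give real opportunities for capture. Section 11.4.3 does not put tenderness in its own list of local reactions; it reports it only from the earlier trial and without a rate. Staff may record tenderness as injection pain. Nothing in the protocol requires the risk section and the solicited list to match.

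Most of this stands and limits the consequence. A reader might infer that a cohort difference confined to these reactions could not be seen. Section 10.6 does not support that. A reader might also infer that fatigue is lost altogether, but the joint Appendix B row points the other way. Nor do the documents establish under-ascertainment as a fact: weaker prompting makes it plausible, and no more.

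Two parts of the reply fall short. The Section 10.6 endpoint counts only what has been elicited, so it does not make up for an absent prompt. And no section says that tenderness is to be recorded as pain, or chills under fever; if that is the intention, it needs to be written down.

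**Conclusion.** The point holds as a gap between Sections 8.1.2 and 11.4.3 and Appendix B. Two of the twelve reaction terms in Section 11.4.3, tenderness and chills, have neither a solicited term nor an Appendix B row. A third, fatigue, needs its label aligned. As written, tenderness and chills are excluded from any reactogenicity summary and may be less completely captured than listed symptoms.

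The size in events cannot be stated. The documents give no frequency for tenderness, chills or fatigue and no rate of unprompted reporting. The exclusion also should not be read as zero events observed in 32 to 35 subjects with a confidence limit attached: it is a classification rule, not data.

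The conclusion rests on a literal reading of Sections 8.1.2 and 8.1.3 and on the case report forms adding no symptom prompts beyond those sections. In an exploratory study whose secondary endpoint takes in all related AEs, this is an inexpensive improvement to the secondary objective rather than a threat to the trial.

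**What to change.** 1. In Section 8.1.2, add injection-site tenderness and chills to the solicited list, and change malaise to fatigue/malaise to agree with Appendix B.
2. Ask about these items by name at the contacts already scheduled: the 30-minute observation and the Day 7 history and injection-site evaluation.
3. Reconcile Section 8.1.2, Section 8.4 with Table 2, Appendix B and Section 11.4.3 so that it is clear which grading scale applies to tenderness, chills and fatigue. Because Grade 3 systemic AEs feed halting rule 4, the sponsor should decide the grading.
4. For subjects vaccinated before the change, show any tenderness, chills or fatigue with onset in Days 0–7 alongside the reactogenicity summary, marked as unprompted and reported by form version. Do not pool them silently with prompted data.

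The cost is a protocol wording change, a few form items at existing contacts and a sponsor decision on grading. No new visit is needed. More mild events will be counted, and pain and tenderness will overlap to some degree, so they should be reported as separate items.

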8.1.3 Unsolicited Events

AEs that are not specifically listed in Section 8.1.2 and not documented in the screening medical history as pre-existing conditions will be categorized as “Other AE’s and identified by asking subjects about any new diagnoses, acute illnesses, worsening of a pre-existing condition, visits to the physician, ER, or hospital, medication use and indication.

8.1.4 Adverse Reaction (AR)

An AE that is caused by the vaccine.

8.1.5 Suspected Adverse Reaction (SAR)

An AE for which there is a reasonable possibility that the vaccine caused the AE. ‘Reasonable possibility’ means that there is evidence to suggest a causal relationship between the vaccine and the AE. A suspected adverse reaction implies a lesser degree of certainty about causality than adverse reaction, which implies a high degree of certainty.

8.1.6 Serious Adverse Events

A SAE is an AE, whether considered related to the investigational vaccine or not, resulting in one of the following outcomes:

1. Death during the period of protocol-defined surveillance.
2. Life threatening event: defined as an event that places a subject at immediate risk of death at the time of the event and does not refer to an event that hypothetically might have caused death were it more severe.

3. Requires hospitalization or prolongation of a hospitalization during the period of protocol-defined surveillance: defined as at least an overnight stay in the hospital for treatment that would have been inappropriate if administered in the outpatient setting.
4. Results in a congenital anomaly or birth defect.
5. Results in a persistent or significant disability or substantial disruption of the ability to conduct normal life functions.
6. Any other important medical event that may not result in death, be life threatening, or require hospitalization, may be considered a serious AE when, based upon appropriate medical judgment, the event may jeopardize the subject and may require medical or surgical intervention to prevent one of the outcomes listed above.

8.1.7 Unexpected Adverse Events

An AE is considered unexpected if it is not listed in the Investigator Brochure or Package Insert (for marketed products) or is not listed at the specificity or severity that has been observed. “Expected” means that the event has previously been observed with the investigational agent and is identified and/or described in the current Investigator’s Brochure (IB) or package insert. It does not mean that the event is expected with pharmacologically similar drugs, the underlying disease(s), or concomitant medications. Such events are considered unexpected for reporting purposes.

8.1.8 Suspected Unexpected Serious Adverse Reaction (SUSAR)

A SUSAR is a Suspected Adverse Reaction that is both Serious and Unexpected.

8.1.9 Unanticipated Problems

An Unanticipated Problem (UP) is any incident, experience, or outcome that is

1. unexpected in terms of nature, severity, or frequency in relation to
 - a. the research risks that are described in the IRB-approved research protocol and informed consent document; Investigator’s Brochure or other study documents; and
 - b. the characteristics of the subject population being studied; and
2. possibly, probably or definitely related to participation in the research; and
3. places subjects or others at a greater risk of harm (including physical, psychological, economic, or social harm) than was previously known or recognized. (Per the IND Sponsor, an AE with a serious outcome will be considered increased risk.)

8.1.10 Serious Unanticipated Problem

A UP that meets the definition of a serious adverse event or compromises the safety, welfare or rights of subjects or others

8.1.11 Unanticipated Problem that is Not an Adverse Event (UPnonAE)

A UP that does not fit the definition of an AE, but which may, in the opinion of the investigator, involve risk to the subject, affect others in the research study, or significantly impact the integrity of research data. For example, report occurrences of breaches of confidentiality, accidental destruction of study records, or unaccounted-for study drug.

8.1.12 Serious Protocol Deviation

A “Protocol Deviation” [see below] that meets the definition of a Serious Adverse Event or compromises the safety, welfare, or rights of subjects or others.

8.1.13 Protocol Deviation

Any change, divergence, or departure from the IRB-approved study procedures in a research protocol. Protocol deviations are further characterized as:

1. Those that occur because a member of the research team deviates from the protocol.
2. Those that are identified before they occur but cannot be prevented.
3. Those that are discovered after they occur.

8.1.14 Non-compliance [Definition is IRB dependent]:

At a Site Overseen by non-NIH IRB: Investigators must follow the definitions, requirements, and reporting procedures per the IRB of record for the study/site where the possible non-compliance event occurred.

8.2 Recording Period for Adverse Events

- All non-serious AEs will be assessed, recorded and reported for 28 days beginning at study vaccination, and will be followed to resolution, even if more than 28 days, or until the PI deems the event to be chronic or the subject to be stable.
 - Solicited non-serious AEs may be assessed/graded per a different table, if specified herein, and may be recorded and reported separately for tracking purposes.
 - Reactogenicity AEs/events are solicited AEs that are collected in the first 7 days after vaccination and may be recorded and reported separately for tracking purposes.
- SAEs, regardless of causality, will be assessed, recorded and reported for 90 days beginning at study vaccination, and will be followed to resolution, even if more than 90 days, or until the PI deems the event to be chronic or the subject to be stable.
- SUSARs, UPs, and UPnonAEs will be assessed, recorded and reported through the end of the study, beginning at study ENROLLMENT, and will be followed to resolution, even if beyond the end of the study (as may be permissible and possible in consultation with the IRB and sponsor) or until the PI deems the event to be chronic or the subject to be stable.

Assessment of safety will include clinical observation and monitoring of clinical and immunologic parameters. Safety will be evaluated by monitoring of subjects for local and systemic adverse reactions within the first 30 minutes post vaccination. Subjects will return to the clinic on Day 7 following vaccination for in-person clinical assessment.

All AEs will be graded for severity and assessed for relationship to the study product. A study clinician will be available 24 hours a day during the study evaluation period. Should a subject call a study clinician to report an AE, it will be fully documented in the subject's study chart and discussed with the PI. Interim follow-up visits (between protocol scheduled visits) may be scheduled at the PI's discretion if additional assessment is indicated.

All AEs will be captured in the source documents and in Clinical Research Information Management System of the NIAID (CRIMSON). Those assessed as serious will be further reported on the Sponsor's SAE-UP report form. The AEs judged to be possibly, probably, or definitely related to the study product will be followed as specified above, generally until resolution.

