2. OBJECTIVES

2.1 Primary Objective:

To explore the difference in the stalk antibody response against Influenza A group 1 stalks as measured by enzyme-linked immunosorbent assay (ELISA) and neutralization titer after receipt of the Monovalent Influenza Subvirion Vaccine (H5N1) in previous recipients of H2N2, H6N1 and H9N2 pLAIVs compared with healthy, pLAIV-naïve individuals.

2.2 Secondary Objective:

Assess the reactogenicity of the Monovalent Influenza Subvirion Vaccine (H5N1) in previous recipients of live attenuated influenza vaccine (LAIV) compared with healthy, pLAIV-naïve individuals.

Adverse events will be assessed, graded and recorded for 28 days after vaccination. Serious Adverse Events (SAEs) will be assessed for 90 days after the immunization.

2.3 Exploratory Objectives:

- To assess the biological activity of antibodies to the HA stalk region by passive transfer of serum from study subjects to mice to assess their ability to protect the mice from lethal challenge with an influenza virus.
- To correlate ELISA and neutralizing stalk antibody titers with functional ability of the post vaccine serum to protect mice from lethal challenge.
- To assess the breadth of the vaccine induced antibody response.
- To assess plasmablast and memory B cell responses to the pISV in the previous pLAIV recipients compared with naïve individuals.
- To assess the longevity of the stalk antibody response.
- To determine the titer of anti-H5 head antibodies in the 2 cohorts of subjects.
- To determine the titer of antibodies directed to the HA head received in the pLAIV doses.

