3.2 Study Schedule

The study will be divided into 3 phases:

1. Screening, eligibility determination and consent up to 60 days prior to vaccination/enrollment (usually 2 visits initiated under a separate institutional review board (IRB)-approved screening protocol)
2. Vaccination/Enrollment (Day 0)
3. Outpatient follow-up at 7, 14, 28, 56, 90, and 360 days post vaccination

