6.8 Study Procedures By Day

See [Appendix A](#) for a tabular representation of study procedures. In the description below, Study Day 0 is the day of receipt of vaccine. The days are numbered thereafter.

Study Day 0 (Day of Vaccination/Enrollment)

1. Verify that study-specific Informed Consent was obtained.
2. Ensure that all inclusion/exclusion criteria are met.
3. Record vital signs (blood pressure, temperature, heart rate, and respiratory rate).
4. Perform an abbreviated history and focused physical examination.
5. For women, obtain urine for β -HCG testing. Ensure the test is negative before proceeding; a positive test will exclude the subject from the trial.
6. Obtain blood for Serum and for PBMCs.
7. Administer the vaccine.
8. Observe for at least 30 minutes after vaccination to evaluate for immediate adverse reactions.
9. Record vital signs (blood pressure, temperature, heart rate, and respiratory rate) 30 minutes after vaccination.
10. Review pregnancy prevention Counseling (Females only).

Study Day 7 \pm 1 Day

1. Obtain interim history and perform focused physical examination, concentrating on any acute complaints and adverse events after vaccination.
2. Assess continuing eligibility and for treatments that could potentially interfere with vaccine-induced immunity.
3. Record vital signs. (blood pressure, temperature, heart rate).
4. Evaluate injection site.
5. Perform an abbreviated history and focused physical examination.
6. Obtain blood for serum and for PBMCs.
7. Review Pregnancy Prevention counseling (Females only).

Study Day 14 \pm 2 Day

1. Obtain interim history concentrating on any acute complaints.

2. Assess continuing eligibility. Review use of any concurrent medications. Assess for treatments that could potentially interfere with vaccine-induced immunity.
3. Perform focused physical exam if indicated.
4. Record vital signs. (blood pressure, temperature, heart rate).
5. Obtain blood for serum and PBMCs.
6. Review pregnancy prevention counseling (Females only).

Study Day 28 ±7 Days

1. Obtain interim history concentrating on any acute complaints.
2. Assess continuing eligibility. Review use of any concurrent medications. Assess for treatments that could potentially interfere with vaccine-induced immunity.
3. Perform focused physical exam if indicated.
4. If female, obtain urine for β -HCG testing.
5. Obtain blood for serum and PBMCs.

Study Day 56 ±7 Days

1. Perform basic history, concentrating on any acute complaints.

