8.4 Assessment of Severity

All AEs will be graded for severity.

- **Solicited AEs will be assessed using the grading system shown in Appendix B: Local and Systemic Adverse Event Grading Systems. This table is based on the NIAID “Division of AIDS (DAIDS) Table for Grading the Severity of Adult and Pediatric Adverse Events,” Version 2.1, March 2017:**
<https://rsc.tech-res.com/docs/default-source/safety/daids-ae-grading-table-.pdf>

- All AEs will be assessed by the study investigators using the grading system shown in Table 2, below:

Table 2: Adverse Event Grading System

Severity	Grade	Defined
None	0	N/A
Mild	1	No effect on activities of daily living, over the counter treatment given $\leq 2x/day$
Moderate	2	Partial limitation in activities of daily living (can complete $\geq 50\%$ baseline, or treatment given $>2x/day$)
Severe)	3	Activities of daily living limited to $<50\%$ of baseline. Medical intervention often required.
Life-threatening	4	Inability to perform basic self-care functions OR severity of illness requires hospitalization

Severity of fever will also be assessed by degree

Table 3: Fever Grading System

Intensity	Grade	Defined
$<100.4^{\circ}\text{F} (<38.0^{\circ}\text{C})$	0	Fever (oral) Temperatures $\geq 100.4^{\circ}\text{F}$, will be confirmed by repeating temperature after waiting 20 minutes
$\geq 100.4^{\circ}\text{F} - 101.4^{\circ}\text{F} (\geq 38.0^{\circ}\text{C} - 38.6^{\circ}\text{C})$	1	
$\geq 101.5^{\circ}\text{F} - 102.4^{\circ}\text{F} (38.7^{\circ}\text{C} - 39.1^{\circ}\text{C})$	2	
$>102.4^{\circ}\text{F} (>39.1^{\circ}\text{C})$	3	

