Appendix B: Local and Systemic Adverse Event Grading Systems

These tables are modified versions of the FDA Toxicity Grading Scale for Healthy Adult and Adolescent Volunteers Enrolled in Preventive Vaccine Clinical Trials to be used to grade adverse events.

Tables for Clinical Abnormalities

Table 4: Local Reaction Grading System

Local Reaction to Injectable Product	Mild (Grade 1)	Moderate (Grade 2)	Severe (Grade 3)	Potentially Life Threatening (Grade 4)
Pain	Does not interfere with activity	Repeated use of non-narcotic pain reliever > 24 hours or interferes with activity	Any use of narcotic pain reliever or prevents daily activity	Emergency room (ER) visit or hospitalization
Pruritus	Does not interfere with activity	Requiring po or topical treatment >24 hrs or IV meds or steroids for ≤ 24 hrs	Requiring IV medication or steroids for >24 hours	ER visit or hospitalization
Erythema/Redness *	2.5 – 5 cm	5.1 – 10 cm	> 10 cm	Necrosis or exfoliative dermatitis
Induration/Swelling**	2.5 – 5 cm and does not interfere with activity	5.1 – 10 cm or interferes with activity	> 10 cm or prevents daily activity	Necrosis

* In addition to grading the measured local reaction at the greatest single diameter, the measurement should be recorded as a continuous variable.

** Induration/Swelling should be evaluated and graded using the functional scale as well as the actual measurement.

Table 5: Vital Signs and Systemic Reactions Grading System

Vital Signs * /Systemic adverse events	Mild (Grade 1)	Moderate(Grade 2)	Severe (Grade 3)	Potentially Life Threatening (Grade 4)
Tachycardia - beats per minute **	101 – 115	116 – 130	> 130	ER visit or hospitalization for arrhythmia
Bradycardia - beats per minute**	50 – 54	45 – 49	< 45	ER visit or hospitalization for arrhythmia
Hypertension (systolic – mm Hg)	141 – 150	151 – 155	> 155	ER visit or hospitalization for malignant hypertension
Hypertension (diastolic) - mm Hg	91 – 95	96 – 100	> 100	ER visit or hospitalization for malignant hypertension
Hypotension (systolic) – mm Hg	85 – 89	80 – 84	< 80	ER visit or hospitalization for hypotensive shock
Respiratory Rate – breaths per minute	17 – 20	21 – 25	> 25	Intubation
Nausea/vomiting	No interference with activity or 1 – 2 episodes/24 hours	Some interference with activity or > 2 episodes/24 hours	Prevents daily activity, requires outpatient IV hydration	ER visit or hospitalization for hypotensive shock

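### Reactogenicity is defined over the first 7 days but has scheduled observations only at 30 minutes and at one Day 7 visit, so fever and reaction size in between rest largely on recall

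*Combined protocol and SAP*

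**What the plan says.** The secondary objective (Sections 2.2 and 10.5) is a cohort comparison: "Assess the reactogenicity of the Monovalent Influenza Subvirion Vaccine (H5N1) in previous recipients of live attenuated influenza vaccine (LAIV) compared with healthy, pLAIV-naïve individuals". Section 8.1.2 sets the window: "Reactogenicity events are solicited adverse events that occur in the first 7 days after vaccination". It lists ten solicited events, and fever is itself defined by an oral temperature threshold.

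Two observations are scheduled in that window:

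- Day 0, Section 6.8: "Observe for at least 30 minutes after vaccination to evaluate for immediate adverse reactions", with vital signs at 30 minutes.
- Day 7 (±1 day), Section 8.2: "Subjects will return to the clinic on Day 7 following vaccination for in-person clinical assessment". Section 6.8 lists an interim history, a focused examination, vital signs including temperature, and the instruction "Evaluate injection site".

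Section 3.2 confirms that nothing is scheduled between them: "Outpatient follow-up at 7, 14, 28, 56, 90, and 360 days post vaccination".

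Some of the scales need a measurement. In Appendix B, erythema is graded by diameter below Grade 4, and the footnote adds that "the measurement should be recorded as a continuous variable". Induration and swelling are graded on size together with function. Table 3 in Section 8.4 grades fever by oral temperature, and a raised reading "will be confirmed by repeating temperature after waiting 20 minutes".

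**The concern.** The scales assume readings that the schedule does not provide. Erythema or fever that starts on Day 1 and is gone by Day 5 is never seen by staff at a scheduled visit, and no tool is given to the subject to record it. What reaches the database is what the subject remembers when asked on Day 6, 7 or 8.

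This bears on what the study sets out to do. Section 10.1 names the estimation of adverse event rates, with 95% confidence intervals, as a purpose, and the secondary endpoint in Section 10.6 counts vaccine-related adverse events by cohort. An event that is forgotten drops out of that count. Section 11.4.3 reports that 84% of adverse events in the earlier placebo-controlled trial were mild, and mild, short events are plausibly the easiest to forget.

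**Working it through.** The plan states no figure on this point, so there is none to reproduce. The check sets the sections side by side; the arithmetic at the end is illustration only.

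**Gap in the schedule.** The visit may fall on Day 6, 7 or 8. The calendar days between Day 0 and the visit are therefore 5 (Days 1–5), 6 (Days 1–6) or 7 (Days 1–7). An event on Day 1 is first asked about 5 to 7 days later. A Day 6 visit also takes place before the 7-day window closes.

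**Capture tools.** Sections 3.2, 6.5, 6.8, 8.2 and Appendix A list no subject-held record, thermometer, ruler, scheduled call or card review. The other routes to Day 1–6 information are:

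- interim history at Days 7, 14 and 28 (recall);
- concomitant medications from vaccination to Day 28 (Section 6.7), although the visit lists in Section 6.8 first name a review of concurrent medications at Day 14;
- a call by the subject to a clinician available 24 hours a day (Section 8.2);
- interim visits at the investigator's discretion (Section 8.2).

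The last two can yield a measurement but are not systematic.

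**Which of the ten solicited events are affected.**

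| Event | Basis of grade | Days 1–6 |
|---|---|---|
| Fever | Oral temperature (Table 3); threshold also defines the event | Needs a reading |
| Erythema | Diameter below Grade 4 | Needs a measurement |
| Swelling, induration | Diameter plus function | Size part needs a measurement |
| Pain, pruritus, headache, malaise, myalgia, nausea | Function, treatment or episodes | Can be graded from history, subject to recall |

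So two events depend on a measurement for the specific scale, two more depend on one in part, and six do not.

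**Illustration of size.** The documents give neither reactogenicity rates by cohort nor a capture fraction, so both are assumed. If a share s of events is captured equally in both cohorts, the observed difference is s × (p1 − p2). Power is for a two-sided 0.05 Fisher exact test by enumeration with 15 v 20 subjects. It gauges precision only; the plan specifies no such test.

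| True rates | s | Observed difference | Power |
|---|---|---|---|
| 50% v 25% | 1 | 25 points | 26% |
| | 0.75 | 18.8 points | 16% |
| | 0.5 | 12.5 points | 9% |
| 70% v 30% | 1 | 40 points | 63% |
| | 0.75 | 30 points | 37% |
| | 0.5 | 20 points | 19% |

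If capture differs by cohort, the observed difference is s1·p1 − s2·p2. With a true 50% in both and capture of 80% v 60%, the rates seen are 0.50 × 0.80 = 40% and 0.50 × 0.60 = 30%, a 10-point difference where none exists.

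**Sampling error for comparison.** At 50% in both cohorts, the 95% half-width of the difference is 1.96 × √(0.25/15 + 0.25/20) = 33 points for 15 v 20, and 1.96 × √(0.25/12 + 0.25/20) = 36 points for 12 v 20.

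**The case against.** The strongest reply is that the gap is narrow and sample size matters more. Much of this stands. Section 8.4 grades all adverse events on a functional scale (Table 2), with temperature as an additional grading for fever. Induration and swelling have a functional scale beside the measurement, and the footnote on recording a continuous value belongs to erythema. The endpoint in Section 10.6 is a count and needs no diameters. Other capture routes exist, and a 10-point recall difference lies well inside the 33 to 36 point half-width. The recall percentages are assumptions throughout.

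Three stronger readings are tempting and are not supported:

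- A reader might infer that reactions in general cannot be graded. Six of the ten solicited events are graded without a measurement.
- A reader might infer that local size grades feed halting rule 4. That rule in Section 8.7 concerns Grade 3 systemic events; of the measured items, only fever is systemic.
- A reader might infer that a recall difference would pass for a vaccine effect. All subjects receive the same H5N1 vaccine (Section 3.5), so the contrast is prior pLAIV. The open-label design leaves room for recall to differ by cohort, but the documents give no direction or size for it.

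What the reply does not remove is that fever and erythema on Days 1–6 have specified scales and no specified means of obtaining the readings. A wide confidence interval reflects random error; it does not correct rates that are too low because events were forgotten. The consent pages were not available to this review and could mention a memory aid, but the procedure list and schedule table are available and show none.

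**Conclusion.** The point holds in a limited form. Within the 7-day window the only scheduled observations are at 30 minutes and at one Day 7 (±1) visit. Fever, erythema and the size component of induration and swelling that come and go between them cannot be reliably graded on Table 3 and Appendix B, and short mild symptoms may be under-counted. The likely direction is downward for the estimated rates. Equal under-capture would shrink a cohort difference; unequal capture could move it either way.

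The size is unknown. The tabulated figures rest on assumed rates and capture fractions, and the conclusion about the schedule does not depend on them. The primary antibody endpoint is untouched. This is an inexpensive improvement to how a secondary objective is measured, and it should be made.

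**What to change.** In Section 6.8 (Day 0) and Appendix A, add a 7-day subject-held card issued with an oral thermometer and a ruler, with one entry a day for each event in Section 8.1.2. Review it at the Day 7 visit. For anyone seen on Day 6, collect the remaining entry at Day 14. State that the card is a source for the existing count of vaccine-related adverse events and for the Appendix B and Table 3 grades. The endpoint need not change; an analysis of each subject's maximum grade over the window is optional.

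If the site already uses such a card, one line in Section 6.8 and a row in Appendix A are enough. If no card is adopted, say that Days 1–6 rest mainly on recall and limit the reporting of measured grades accordingly.

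The cost is a card, thermometer and ruler for about 35 subjects, a few minutes at visits already planned, and IRB review of the card. No visit or staff is added. The card would reduce reliance on memory but would not remove reporting differences that come from open-label knowledge of cohort.
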